13.5.3. Reporting Standards for Pharmacokinetic

Pharmacokinetic Concentration Data	
PC Windows Non-Linear (WNL) File	PC WNL file (CSV format) for the non compartmental analysis by Clinical Pharmacology Modelling and Simulation function will be created according to Standards for the Transfer and Reporting of PK Data document. Note: Concentration values will be imputed as per GUI_51487
Descriptive Summary Statistics, Graphical Displays and Listings	Refer to the GSK Standard PK Display Standard. Refer to the GSK Standard Statistical Display Principle 6.06.1. Note: Concentration values will be imputed as per GUI_51487 for descriptive summary statistics/analysis and summarized graphical displays only.
Pharmacokinetic Parameter Derivation	
PK Parameter to be Derived by Programmer	
The following PK parameters will be derived by the Programmer:
 
 Relative bioavailability (Treatment B / Treatment A) of AUC(0-24), AUC(0-inf), and Cmax Food Effect (Treatment B / Treatment C) of AUC(0-24), AUC(0-inf), and Cmax Predicted Dose accumulation of AUC single dose AUC $Rp = \frac{AUC(0 - \infty)}{AUC(0 - 24)}$
Pharmacokinetic Parameter Data	
Is NQ impacted PK Parameters Rule Being Followed	Yes, refer to Standards for Handling NQ Impacted PK Parameters.
Descriptive Summary Statistics, Graphical Displays and Listings	Refer to GSK Standard PK Display Standard.
Untransformed PK parameter	tmax (TMAX), tlast (TLST), tlag (TLAG).
PK parameter listed only	lambda_z (LAMZ), lambda_z_lower (LAMZL), lambda_x_upper (LAMZU), No_points_lambda_z (LAMZNPT).

13.6. Appendix 6: Derived and Transformed Data

13.6.1. General

Multiple Measurements at One Analysis Time Point

 Mean of the measurements will be calculated and used in any derivation of summary statistics but if listed, all data will be presented. Participants having both High and Low values for Normal Ranges at any post-baseline visit for safety parameters will be counted in both the High and Low categories of “Any visit post-baseline” row of related summary tables. This will also be applicable to relevant Potential Clinical Importance summary tables.
Study Day

 Calculated as the number of days from First Dose Date: 
 Ref Date = Missing → Study Day = Missing Ref Date < First Dose Date → Study Day = Ref Date – First Dose Date Ref Date ≥ First Dose Date → Study Day = Ref Date – (First Dose Date) + 1

13.6.2. Study Population

Treatment Compliance
Extent of Exposure

 Number of days of exposure to study drug will be calculated based on the formula: Duration of Exposure in Days = Treatment Stop Date – (Treatment Start Date) + 1 Participants who were randomized but did not report a treatment start date will be categorised as having zero days of exposure. The cumulative dose will be based on the formula: Cumulative Dose = Sum of (Number of Days x Total Daily Dose) If there are any treatment breaks during the study, exposure data will be adjusted accordingly.

13.6.3. Safety

Adverse Events
AEs of Special Interest

 While VH3739937 does not have a defined list of AESI, the AESI for the similar compound GSK3640254 will be used for this study (apart from “HIV-1 resistance to GSK3640254” which is not applicable to this study of healthy volunteers). Details of specific SOCs and SMQs for AESI of GSK3640254 are maintained by that compound’s SRT. The list broadly includes the following items: 
 QT prolongation GI intolerance/toxicity Psychiatric events 
 Suicidal ideation/behaviour Depression Bipolar disorder Psychosis Anxiety Sleep disorders Nervous system disorders

ECG Parameters	
RR Interval	

 IF RR interval (msec) is not provided directly, then RR can be derived as : 
 [1] If QTcB is machine read & QTcF is not provided, then : $RR = \left[\left(\frac{QT}{QTcB} \right)^2 \right] * 1000$ 	

 [2] If QTcF is machine read and QTcB is not provided, then : $RR = \left[\left(\frac{QT}{QTcF} \right)^3 \right] * 1000$	
Corrected QT Intervals	

 When not entered directly in the eCRF, corrected QT intervals by Bazett's (QTcB) and Fredericia's (QTcF) formulas will be calculated, in msec, depending on the availability of other measurements. IF RR interval (msec) is provided then missing QTcB and/or QTcF will be derived as : $QTcB = \frac{QT}{\sqrt{\frac{RR}{1000}}}$ $QTcF = \frac{QT}{3\sqrt{\frac{RR}{1000}}}$	

13.6.4. Pharmacokinetic

Derived pharmacokinetic data is described in Section 8.1.1.2. Additionally, daily dose accumulation from single dose data (Part 1) for AUC will be predicted as follows:

$$Rp = \frac{AUC(0 - \infty)}{AUC(0 - 24)}$$

13.6.5. Pharmacodynamic

No pharmacodynamic endpoints will be derived or transformed.

13.6.6. Laboratory

If a laboratory value which is expected to have a numeric value for summary purposes, has a non-detectable level reported in the database, where the numeric value is missing, but typically a character value starting with '<x' or '>x' (or indicated as less than x or greater than x in the comment field) is present, the number of significant digits in the observed values will be used to determine how much to add or subtract in order to impute the corresponding numeric value.

- Example 1: 2 Significant Digits = '< x ' becomes x - 0.01
- Example 2: 1 Significant Digit = '> x' becomes x + 0.1
- Example 3: 0 Significant Digits = '< x' becomes x - 1

13.7. Appendix 7: Reporting Standards for Missing Data

13.7.1. Premature Withdrawals

Element	Reporting Detail
General	
 Participant study completion was defined as complete if he/she has completed all phases of the study including the last visit and the last scheduled procedure shown in the schedule of activities Withdrawn participants may be replaced in the study depending on study part and whether adequate sample size for a cohort as already been reached. All available data from participants who were withdrawn from the study will be listed and all available planned data will be included in summary tables and figures, unless otherwise specified.

13.7.2. Handling of Missing Data

Element	Reporting Detail
General	
 Missing data occurs when any requested data is not provided, leading to blank fields on the collection instrument: 
 These data will be indicated by the use of a “blank” in participant listing displays. Unless all data for a specific visit are missing in which case the data is excluded from the table. Answers such as “Not applicable” and “Not evaluable” are not considered to be missing data and should be displayed as such.
Outliers	
 Any participants excluded from the summaries and/or statistical analyses will be documented along with the reason for exclusion in the clinical study report.

13.7.2.1. Handling of Missing and Partial Dates

Element	Reporting Detail		
General	
 Partial dates will be displayed as captured in participant listing displays. Where necessary, display macros may impute dates as temporary variables for sorting data in listings only. In addition, partial dates may be imputed for ‘slotting’ data to study phases (see Section 13.4.1) or for specific analysis purposes as outlined below. Imputed partial dates will not be used to derive study day, time to onset or duration (e.g., time to onset or duration of adverse events), or elapsed time variables (e.g., time since diagnosis). In addition, imputed dates are not used for deriving the last contact date in overall survival analysis dataset. 		
Adverse Events	
 Imputations in the adverse events dataset are used for slotting events to the appropriate study time periods and for sorting in data listings. Partial dates for AE recorded in the CRF will be imputed using the following conventions: 
 
 Missing start day	 
 If study treatment start date is missing (i.e. participant did not start study treatment), then set start date = 1st of month. Else if study treatment start date is not missing: 
 If month and year of start date = month and year of study treatment start date then 	
 
 	Missing start day	
 If study treatment start date is missing (i.e. participant did not start study treatment), then set start date = 1st of month. Else if study treatment start date is not missing: 
 If month and year of start date = month and year of study treatment start date then
Missing start day	
 If study treatment start date is missing (i.e. participant did not start study treatment), then set start date = 1st of month. Else if study treatment start date is not missing: 
 If month and year of start date = month and year of study treatment start date then 		

Element	Reporting Detail	
		
 ▪ If stop date contains a full date and stop date is earlier than study treatment start date then set start date= 1st of month. ▪ Else set start date = study treatment start date. ○ Else set start date = 1st of month.
	Missing start day and month	
 • If study treatment start date is missing (i.e. participant did not start study treatment), then set start date = January 1. • Else if study treatment start date is not missing: 
 ○ If year of start date = year of study treatment start date then 
 ▪ If stop date contains a full date and stop date is earlier than study treatment start date then set start date = January 1. ▪ Else set start date = study treatment start date. ○ Else set start date = January 1.
	Missing stop day	Last day of the month will be used.
	Missing stop day and month	No Imputation
	Completely missing start/end date	No imputation
	
 • Completely missing start or end dates will remain missing, with no imputation applied. 	
Concomitant Medications/Medical History	
 • Partial dates for any concomitant medications recorded in the CRF will be imputed using the following convention: 	
	Missing start day	
 • If study treatment start date is missing (i.e. participant did not start study treatment), then set start date = 1st of month. • Else if study treatment start date is not missing: 
 ○ If month and year of start date = month and year of study treatment start date then 
 ▪ If stop date contains a full date and stop date is earlier than study treatment start date then set start date= 1st of month. ▪ Else set start date = study treatment start date. ○ Else set start date = 1st of month.
	Missing start day and month	
 • If study treatment start date is missing (i.e. participant did not start study treatment), then set start date = January 1. • Else if study treatment start date is not missing: 
 ○ If year of start date = year of study treatment start date then 
 ▪ If stop date contains a full date and stop date is earlier than study treatment start date then set start date = January 1. ▪ Else set start date = study treatment start date. • Else set start date = January 1.
	Missing end day	A '28/29/30/31' will be used for the day (dependent on the month and year)
	Missing end day and month	A '31' will be used for the day and 'Dec' will be used for the month.
	Completely missing start/end date	No imputation
	
 • The recorded partial date will be displayed in listings. 	

13.8. Appendix 8: Values of Potential Clinical Importance

13.8.1. Laboratory Values

Element	Reporting Detail
Laboratory Values and Adverse Events	
 The Division of AIDS (DAIDS) grading for severity of laboratory toxicities and clinical adverse events, version 2.1, July 2017 will be used to assign grades to laboratory values. When deriving the Grading for severity of laboratory toxicity only numeric criteria are considered. The following note will be included in the listing including laboratory severity output: "Grades were derived based on numeric criteria as defined in DAIDS Version 2.1 and did not take into consideration of clinical signs or symptoms which is needed for the final grade associated with the adverse event." Reference ranges for all laboratory parameters collected throughout the study are provided by the laboratory. A laboratory value that is outside the reference range is considered either high abnormal (value above the upper limit of the reference range) or low abnormal (value below the lower limit of the reference range). Note: a high abnormal or low abnormal laboratory value is not necessarily of clinical concern. The laboratory reference ranges will be provided on the listings of laboratory data. Clinical laboratory test results outside of the reference range will be flagged in the listings.

13.8.2. Urinalysis Values

A participant is considered to have urinalysis results of PCI, if there is an increase in Protein or an increase in Occult Blood results during the study, or if microscopy is performed.

13.8.3. ECG

ECG Parameter	Units	Clinical Concern Range	
		Lower	Upper
Absolute			
Absolute QTcF Interval	msec	< 320	> 450
Absolute PR Interval	msec	< 120	> 200
Absolute QRS Interval	msec	< 75	> 110
Heart Rate	bpm	< 40	> 110
Change from Baseline			
Increase from Baseline QTcF	msec		>60

13.8.4. Vital Signs

Vital Sign Parameter (Absolute)	Units	Clinical Concern Range	
		Lower	Upper
Systolic Blood Pressure	mmHg	< 85	> 160
Diastolic Blood Pressure	mmHg	< 45	> 100
Heart Rate	bpm	< 40	> 110

Vital Sign Parameter (Change from Baseline)	Units	Clinical Concern Range	
		Decrease	Increase
Systolic Blood Pressure	mmHg	≥ 40	≥ 40
Diastolic Blood Pressure	mmHg	≥ 20	≥ 20
Heart Rate	bpm	≥ 30	≥ 30

13.9. Appendix 9: Abbreviations & Trade Marks

13.9.1. Abbreviations

Abbreviation	Description
ADaM	Analysis Data Model
AE	Adverse Event
AIC	Akaike's Information Criteria
A&R	Analysis and Reporting
CDISC	Clinical Data Interchange Standards Consortium
CI	Confidence Interval
CPMS	Clinical Pharmacology Modelling & Simulation
CS	Clinical Statistics
CSR	Clinical Study Report
CTR	Clinical Trial Register
CV _b / CV _w	Coefficient of Variation (Between) / Coefficient of Variation (Within)
DBF	Database Freeze
DBR	Database Release
DOB	Date of Birth
DP	Decimal Places
eCRF	Electronic Case Record Form
EMA	European Medicines Agency
FDA	Food and Drug Administration
FDAAA	Food and Drug Administration Clinical Results Disclosure Requirements
GSK	GlaxoSmithKline
IA	Interim Analysis
ICH	International Conference on Harmonization
IDMC	Independent Data Monitoring Committee
IDSL	Integrated Data Standards Library (GSK Standards Library)
IMMS	International Modules Management System
IP	Investigational Product
ITT	Intent-To-Treat
MMRM	Mixed Model Repeated Measures
PCI	Potential Clinical Importance
PD	Pharmacodynamic
PDMP	Protocol Deviation Management Plan
PK	Pharmacokinetic
PP	Per Protocol
PopPK	Population PK
QC	Quality Control
QTcF	Frederica's QT Interval Corrected for Heart Rate
QTcB	Bazett's QT Interval Corrected for Heart Rate
RAP	Reporting & Analysis Plan
RAMOS	Randomization & Medication Ordering System
SAC	Statistical Analysis Complete
SDSP	Study Data Standardization Plan

Abbreviation	Description
SDTM	Study Data Tabulation Model
SOP	Standard Operation Procedure
TA	Therapeutic Area
TFL	Tables, Figures & Listings

13.9.2. Trademarks

Trademarks of the GlaxoSmithKline Group of Companies	Trademarks not owned by the GlaxoSmithKline Group of Companies
None	[NONMEM] [SAS] [WinNonlin]

13.10. Appendix 10: List of Data Displays

All data displays will use the term “subject” rather than “participant” in accordance with CDSIC and GSK Statistical Display Standards.

13.10.1. Data Display Numbering

The following numbering will be applied for RAP generated displays:

Section	Tables	Figures
Study Population	1.1 to 1.44	NA
Safety	3.1 to 3.35	NA
Pharmacokinetic	4.1 to 4.10	4.1 to 4.20
Section	Listings	
ICH Listings	1 to 16	
Other Listings	17 to 34	

13.10.2. Mock Example Shell Referencing

Nonstandard specifications will be referenced as indicated and if required example mock-up displays provided in [Appendix 11: Example Mock Shells for Data Displays](#).

Section	Figure	Table	Listing
Pharmacokinetic (PK)	PK_F1	PK_T1 PK_T2 PK_T3 PK_T4 PK_T5	NA
Safety	NA	NA	SAFE_L1

13.10.3. Deliverables

Delivery [Priority] [1]	Description
HL	Headline Data Delivery
SAC [1]	Final Statistical Analysis Complete

NOTES:

1. Indicates priority (i.e. order) in which displays will be generated for the reporting effort

13.10.4. Study Population Tables

Study Population Tables					
No.	Population	GSK Standard / Example Shell	Title	Programming Notes	Deliverable [Priority]
Subject Disposition					
1.1.	Safety	ES1xo	Summary of Subject Status and Subject Disposition for the Study Conclusion Record – Part 1	ICH E3, FDAAA, EudraCT	SAC [1], HL
1.2.	Safety	ES1	Summary of Subject Status and Subject Disposition for the Study Conclusion Record – Part 2	ICH E3, FDAAA, EudraCT	SAC [1], HL
1.3.	Safety	ES1xo	Summary of Subject Status and Subject Disposition for the Study Conclusion Record – Part 3	ICH E3, FDAAA, EudraCT	SAC [1], HL
1.4.	Safety	ES1xo	Summary of Subject Status and Subject Disposition for the Study Conclusion Record Related to COVID-19 Pandemic – Part 1	ICH E3, FDAAA, EudraCT	SAC [1]
1.5.	Safety	ES1	Summary of Subject Status and Subject Disposition for the Study Conclusion Record Related to COVID-19 Pandemic – Part 2	ICH E3, FDAAA, EudraCT	SAC [1]
1.6.	Safety	ES1xo	Summary of Subject Status and Subject Disposition for the Study Conclusion Record Related to COVID-19 Pandemic – Part 3	ICH E3, FDAAA, EudraCT	SAC [1]
1.7.	Safety	SD1	Summary of Treatment Status and Reasons for Discontinuation of Study Treatment– Part 1	ICH E3, Treatment group column will indicate treatment sequence to which the subject was assigned. Add Footnote: Since Part 1 only has a single dose per period, a participant's treatment status is complete if they take any dose within any period.	SAC [1]

Study Population Tables					
No.	Population	GSK Standard / Example Shell	Title	Programming Notes	Deliverable [Priority]
1.8.	Safety	SD1	Summary of Treatment Status and Reasons for Discontinuation of Study Treatment – Part 2	ICH E3, Treatment group column will indicate the treatment that the subject was taking at the time of discontinuation	SAC [1]
1.9.	Safety	SD1	Summary of Treatment Status and Reasons for Discontinuation of Study Treatment – Part 3	ICH E3, Treatment group column will indicate the treatment that the subject was taking at the time of discontinuation Add Footnote: Since Part 3 only has a single dose per period, a participant's treatment status is complete if they take any dose within any period.	SAC [1]
1.10.	Safety	SD1	Summary of Treatment Status and Reasons for Discontinuation of Study Treatment Related to COVID-19 Pandemic– Part 1	ICH E3, Treatment group column will indicate the treatment that the subject was taking at the time of discontinuation Add Footnote: Since Part 1 only has a single dose per period, a participant's treatment status is complete if they take any dose within any period.	SAC [1]
1.11.	Safety	SD1	Summary of Treatment Status and Reasons for Discontinuation of Study Treatment Related to COVID-19 Pandemic – Part 2	ICH E3, Treatment group column will indicate the treatment that the subject was taking at the time of discontinuation	SAC [1]

Study Population Tables					
No.	Population	GSK Standard / Example Shell	Title	Programming Notes	Deliverable [Priority]
1.12.	Safety	SD1	Summary of Treatment Status and Reasons for Discontinuation of Study Treatment Related to COVID-19 Pandemic – Part 3	ICH E3, Treatment group column will indicate the treatment that the subject was taking at the time of discontinuation Add Footnote: Since Part 3 only has a single dose per period, a participant's treatment status is complete if they take any dose within any period.	SAC [1]
1.13.	Safety	ES4	Summary of Subject Disposition at Each Study Period– Part 1	ICH E3	SAC [1]
1.14.	Safety	ES4	Summary of Subject Disposition at Each Study Period– Part 2	ICH E3	SAC [1]
1.15.	Safety	ES4	Summary of Subject Disposition at Each Study Period– Part 3	ICH E3	SAC [1]
1.16.	Safety	ES5	Summary of Reason for Withdrawal at Each Period – Part 1	FDAAA, EudraCT	SAC [1]
1.17.	Safety	ES5	Summary of Reason for Withdrawal at Each Period – Part 2	FDAAA, EudraCT	SAC [1]
1.18.	Safety	ES5	Summary of Reason for Withdrawal at Each Period – Part 3	FDAAA, EudraCT	SAC [1]
1.19.	Screened	ES6	Summary of Screening Status and Reasons for Screen Failure	Journal Requirements.	SAC [1]
1.20.	Safety	ES11	Summary of Outcome of Adverse Events Which Led to Study Withdrawal at Each Study Period – Part 1	EudraCT	SAC [1]
1.21.	Safety	ES11	Summary of Outcome of Adverse Events Which Led to Study Withdrawal at Each Study Period – Part 2	EudraCT	SAC [1]

CONFIDENTIAL

212548

Study Population Tables					
No.	Population	GSK Standard / Example Shell	Title	Programming Notes	Deliverable [Priority]
1.22.	Safety	ES11	Summary of Outcome of Adverse Events Which Led to Study Withdrawal at Each Study Period – Part 3	EudraCT	SAC [1]
1.23.	Enrolled	NS1	Summary of Number of Subjects by Country and Site ID – Part 1	EudraCT/Clinical Operations	SAC [1]
1.24.	Enrolled	NS1	Summary of Number of Subjects by Country and Site ID – Part 2	EudraCT/Clinical Operations	SAC [1]
1.25.	Enrolled	NS1	Summary of Number of Subjects by Country and Site ID – Part 3	EudraCT/Clinical Operations	SAC [1]
1.26.	Enrolled	NS1	Summary of Number of Subjects by Country and Site ID Relative to COVID-19 Pandemic Measures – Part 1		SAC [1]
1.27.	Enrolled	NS1	Summary of Number of Subjects by Country and Site ID Relative to COVID-19 Pandemic Measures – Part 2		SAC [1]
1.28.	Enrolled	NS1	Summary of Number of Subjects by Country and Site ID Relative to COVID-19 Pandemic Measures – Part 3		SAC [1]
Protocol Deviation					
1.29.	Safety	DV1	Summary of Important Protocol Deviations – Part 1	ICH E3	SAC [1]
1.30.	Safety	DV1	Summary of Important Protocol Deviations – Part 2	ICH E3	SAC [1]
1.31.	Safety	DV1	Summary of Important Protocol Deviations – Part 3	ICH E3	SAC [1]
1.32.	Safety	DV1	Summary of Important Protocol Deviations and Relation with COVID-19 -Part 1	ICH E3	SAC [1]
1.33.	Safety	DV1	Summary of Important Protocol Deviations and Relation with COVID-19 -Part 2	ICH E3	SAC [1]
1.34.	Safety	DV1	Summary of Important Protocol Deviations and Relation with COVID-19 -Part 3	ICH E3	SAC [1]

Study Population Tables					
No.	Population	GSK Standard / Example Shell	Title	Programming Notes	Deliverable [Priority]
Population Analysed					
1.35.	Screened	SP1	Summary of Study Populations	GSK Statistical Display Standard.	SAC [1]
Demographic and Baseline Characteristics					
1.36.	Safety	DM1xo	Summary of Demographic Characteristics – Part 1	ICH E3, FDAAA, EudraCT	SAC [1]
1.37.	Safety	DM1	Summary of Demographic Characteristics – Part 2	ICH E3, FDAAA, EudraCT	SAC [1]
1.38.	Safety	DM1xo	Summary of Demographic Characteristics – Part 3	ICH E3, FDAAA, EudraCT	SAC [1]
1.39.	Enrolled	DM11xo	Summary of Age Ranges – Part 1	EudraCT	SAC [1]
1.40.	Enrolled	DM11	Summary of Age Ranges – Part 2	EudraCT	SAC [1]
1.41.	Enrolled	DM11xo	Summary of Age Ranges – Part 3	EudraCT	SAC [1]
1.42.	Safety	DM6xo	Summary of Race and Racial Combination Details – Part 1	ICH E3, FDA, FDAAA, EudraCT	SAC [1]
1.43.	Safety	DM6	Summary of Race and Racial Combination Details – Part 2	ICH E3, FDA, FDAAA, EudraCT	SAC [1]
1.44.	Safety	DM6xo	Summary of Race and Racial Combination Details – Part 3	ICH E3, FDA, FDAAA, EudraCT	SAC [1]

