For Part 2 MAD Cohorts 3, 4 and 5, 24-hour continuous Holter/ECG recordings will be collected, on the day before the first dose (Day -1), Day 1, and Day 14 for extraction of ECGs paired with PK sampling. In addition, 12-Lead ECGs will be collected for Part 2 at timepoints indicated in the SoA.

Participants in Part 2 will have a screening visit within 28 days prior to first dose and a follow-up visit approximately 28 days after the last dose. Flexibility of visit scheduling may be required if a pandemic situation applies (see [Appendix 7](#)). Otherwise, study assessments will be performed as indicated in [SoA](#). Study participants will be confined to the clinic from Day -2 until discharge with requirement to complete all scheduled outpatient visits. Maximum duration of study participation from admission into the unit until completion of follow visit will be approximately 5 weeks.

Part 3 (RBA):

Part 3 is a randomized, open-label, single-dose, 3-period crossover optional Cohort 7 to compare the RBA of the GSK3739937 PiB with GSK3739937 Tablet and to assess the effect of food on the safety, tolerability and PK of GSK3739937 Tablet in healthy participants. In Part 3, approximately 18 participants will be treated to ensure that 12 evaluable participants complete Cohort 7. If participants prematurely discontinue Part 3, additional participants may be randomized after consultation with the sponsor to ensure that 12 evaluable participants complete the study.

Part 3 will consist of a screening period and 3 sequential treatment periods with a single dose of study intervention per treatment period.

Prior to dosing on Day 1 of Period 1, participants will be randomly assigned to 1 of 3 treatment sequences (ABC, BAC or CAB). Participants will receive each of the following treatments administered as 1 treatment per period:

- Treatment A: GSK3739937 PiB, 100 mg (administered as oral suspension) administered under moderate fat conditions (reference)
- Treatment B: GSK3739937 Tablet, 100 mg (single dose given as a 100 mg tablet(s)) administered under moderate fat conditions (test)
- Treatment C: GSK3739937 Tablet, 100 mg (single dose given as 100 mg tablet(s)) administered under fasted conditions (reference).

To ensure adequate washout, there will be at least 24 days between each dose of study intervention, with an allowance window of 4 hours (i.e., 24 days minus 4 hours) to allow flexibility in scheduling participants for dosing at the clinic.

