The SAD portion of the study will be conducted in an interlocking fashion with two separate cohorts each of approximately 9 healthy participants. Each of these two cohorts may contain a minimum of three escalating doses of VH3739937 through to 640 mg. An additional 800 mg dose will be evaluated as this was indicated following review of safety and PK data from participants dosed up to 640 mg. The interlocking design shown in [Figure 3](#) and the randomization sequence in [Table 7](#) will allow the 9 participants in each cohort to potentially receive one of the lower and one of the higher doses of VH3739937. Participants in Cohort 1 and Cohort 2 will follow the same randomization strategy with alternating ascending doses ([Table 7](#)). In each escalating dose period, 6 participants will be randomized to receive VH3739937 and 3 participants will be randomized to receive placebo. Participants in either Cohort will be assigned to one of the three treatment sequences, and each participant will receive placebo at least once. When the 800 mg dose is evaluated, 6 participants from both Cohorts 1 and 2 will be randomized to receive VH3739937 and 3 participants will be randomized to receive placebo, independent of which prior doses they received.

Details of the starting dose and dose escalation can be found in Section 4.3

Table 7 Description of treatment sequences in Cohort 1 and Cohort 2 Periods 1, 2, and 3

Cohort 1	Period 1	Period 2	Period 3
Sequence 1	Placebo	Dose 3	Dose 5
Sequence 2	Dose 1	Placebo	Dose 5
Sequence 3	Dose 1	Dose 3	Placebo

Cohort 2	Period 1	Period 2	Period 3
Sequence 1	Placebo	Dose 4	Dose 6
Sequence 2	Dose 2	Placebo	Dose 6
Sequence 3	Dose 2	Dose 4	Placebo

For Part 1, 24-hour continuous Holter/ ECG recordings will be collected on the day before dosing (Day -1), and Day 1 for extraction of ECGs paired with PK sampling.

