6. STUDY INTERVENTION

Study intervention is defined as any investigational intervention(s), marketed product(s), placebo, or medical device(s) intended to be administered to a study participant according to the study protocol. The active investigation interventions used in study 212548 are GSK3733937 Powder in bottle (PiB) and GSK3733937 Tablet, 100 mg (can also be referred to as VH3733973 PiB and VH 3739937 Tablet, 100 mg)

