2.3. Study Design

Overview of Study Design and Key Features	
	
placebo (PBO) for 14 consecutive days (cohorts 3 and 4), or for 18 consecutive days (cohort 5). Participants in Cohort 6 will receive one dose per week for 3 consecutive weeks.
 
 • The duration of dosing in Cohort 5 is to support up to 18-day dosing as an oral lead in for the future SAD and MAD studies of the long acting formulation of VH3739937. This duration is to potentially allow the identification of any early drug hypersensitivity reactions (HSR) which may occur before the administration of the long acting formulation. • In each escalating dose cohort, 7 participants will be randomized to receive VH3739937 and 3 participants will be randomized to receive PBO 
Part 3 (RBA/FE)
 
 • Part 3 is a randomized, open-label, single-dose, 3-period crossover Cohort 7 to compare the RBA of the PiB formulation of VH3739937 with the tablet formulation and to assess the effect of food on the safety, tolerability and PK of the tablet formulation in healthy participants. • In Part 3, approximately 18 participants will be treated to ensure that 12 evaluable participants complete Cohort 7.

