4. ANALYSIS POPULATIONS

Population	Definition / Criteria	Analyses Evaluated
Screened	
 • All participants who were screened for eligibility 	
 • Study Population
Enrolled	
 • All participants who passed screening and entered the study. • Note screening failures (who never passed screening even if rescreened) and participants screened but never enrolled into the study (Reserve, Not Used) are excluded from the Enrolled population as they did not enter the study. 	
 • Study Population
Safety	
 • All randomized participants who received at least one dose of study treatment. • Participants will be analyzed according to the intervention they received. 	
 • Study Population • Safety
Pharmacokinetic (PK)	
 • The PK Population will include all participants who undergo plasma or urine PK sampling and have evaluable PK assay results. 	
 • PK analyses

Refer to [Appendix 10](#) which details the population used for each display.

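### In SAP Tables 1.7, 1.9, 1.10 and 1.12 the completion footnote repeats the Safety-population entry rule, so these tables must show 100% treatment completion in Parts 1 and 3

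*SAP*

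**What the plan says.** SAP section 13.10.4 lists summaries of treatment status and reasons for stopping study treatment. Tables 1.7 (Part 1) and 1.9 (Part 3) are the main versions, and Tables 1.10 and 1.12 are the COVID-19 versions. All four name the Safety population.

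- Part 1 footnote (Tables 1.7 and 1.10): "Since Part 1 only has a single dose per period, a participant's treatment status is complete if they take any dose within any period".
- Part 3 footnote (Tables 1.9 and 1.12), after the same opening clause for Part 3: "a participant's treatment status is complete if they take any dose within any period".
- Safety population, SAP section 4: "All randomized participants who received at least one dose of study treatment".
- Placebo is study intervention under Protocol section 6, whose definition includes "placebo, or medical device(s) intended to be administered to a study participant according to the study protocol". A placebo dose therefore satisfies both rules.

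More than one dose is planned for most of these participants. For Part 3 the Protocol synopsis says: "Participants will receive each of the following treatments administered as 1 treatment per period". For Part 1, Protocol section 4.1 says: "Participants in either Cohort will be assigned to one of the three treatment sequences, and each participant will receive placebo at least once". Each of those sequences has three periods (Protocol Table 7).

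The programming notes for Tables 1.9, 1.10 and 1.12 ask for the treatment the participant was on when discontinuing. SAP section 11.1.1 says that discontinuation reasons will be split by whether they were due to the pandemic. Study completion is defined separately in SAP section 13.7.1, as completing all phases through the last visit.

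**The concern.** A table of treatment status should separate participants who took their planned treatment from those who stopped, and say why they stopped. Here the completion rule is met by the single dose that puts a participant in the table. Someone dosed in Period 1 and then stopped, for an adverse event or any other reason, is counted as having completed treatment.

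The tables then cannot deliver what the plan asks of them: the reasons in their titles, the treatment at discontinuation, or the COVID-19 split. Safety and tolerability are primary objectives, and a reader who takes Table 1.7 or 1.9 alone would see no treatment discontinuation in two of the three study parts. The same report could show a withdrawal in Table 1.18 beside 100% completion in Table 1.9.

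**Working it through.** The plan states no figure for this point, so there is nothing to reproduce. The check is logical, followed by simple counts.

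**1. The two conditions.** Let *d* be the number of periods in which a participant was dosed.

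- In the Safety population: *d* ≥ 1 (SAP section 4).
- Complete under the footnote: a dose in any period, that is *d* ≥ 1 (SAP section 13.10.4).

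The conditions are identical, so the not-complete count is zero for any data.

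**2. Enumeration.** With *k* planned periods there are 2^*k* dosed/not-dosed patterns, of which 2^*k* − 1 contain at least one dose. Only one pattern has every planned dose, so 2^*k* − 2 Safety patterns lack at least one.

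| Planned periods | In Safety | Complete by footnote | Not complete by footnote | Not complete if all planned doses are required |
|---|---|---|---|---|
| 3 (Part 3; Part 1 Cohorts 1 and 2) | 7 | 7 | 0 | 6 |
| 4 (Part 1 plus 800 mg) | 15 | 15 | 0 | 14 |
| 1 (800 mg only) | 1 | 1 | 0 | 0 |

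The rule does no harm where only one period is planned. It fails wherever two or more are.

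**3. Reading the footnote period by period.** On this reading each dosed period is complete. A participant who stops after Period 1 has one complete period and no period recorded as discontinued, so the count is still zero. Only counting missed periods would change it, and the footnote does not provide for that.

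**4. Whether stopping between periods is foreseen.** It is. The Protocol synopsis has Part 1 replacements join the sequence at the point where the departing participant left it. Protocol sections 7.1.1 and 7.1.2 stop study treatment on liver and QTcF criteria. Protocol section 8.1.3 asks the investigator to consider stopping study drug in moderate to severe COVID-19.

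**5. Possible size in Part 3.** SAP section 2.3 says: "In Part 3, approximately 18 participants will be treated to ensure that 12 evaluable participants complete Cohort 7". The allowance is 18 − 12 = 6. The documents give no dropout rate, so the number of early stops is an assumption, taken from 0 to 6:

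| Early stops | Shown under the footnote | Shown if all planned doses are required |
|---|---|---|
| 0 | 0/18 | 0/18 |
| 1 | 0/18 | 1/18 = 5.6% |
| 3 | 0/18 | 3/18 = 16.7% |
| 6 | 0/18 | 6/18 = 33.3% |

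**The case against.** The strongest defence is that early stopping is reported elsewhere. Tables 1.1 and 1.3 give study conclusion status. Tables 1.13 and 1.15 give disposition by period, and Tables 1.16 and 1.18 give withdrawal reasons by period. Tables 3.19 and 3.21 give adverse events leading to permanent discontinuation or withdrawal, and are headline deliverables, which Tables 1.7 and 1.9 are not. Listings 1, 2, 9, 14 and 18 carry the individual data without this footnote. A reader might infer that tolerability information, or the identity of those who did not supply all Part 3 periods, is lost. The documents do not support that, and this part of the defence stands.

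The second argument is that the convention is disclosed and has a reason: once a single dose is taken, no ongoing course remains to interrupt. That is fair within a period. It does not carry over to a planned sequence of three doses, and Table 1.7 is itself laid out by assigned sequence. Nor does study withdrawal cover every case, because the liver and QTcF rules stop treatment, and a participant could stop dosing without leaving the study.

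Third, a reader might take 6/18 as an expected discontinuation rate. It is not. It is the ceiling implied by a planning allowance for evaluable completers, and a participant can lack evaluable PK without missing a dose.

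**Conclusion.** The point holds for four tables. As written, Tables 1.7, 1.9, 1.10 and 1.12 show 100% treatment completion and no discontinuation reasons in Parts 1 and 3, regardless of the data. This follows from the two definitions alone.

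The consequence is a reporting inconsistency. If anyone stops between periods, these tables will conflict with whichever of Tables 1.13, 1.15, 1.16, 1.18, 3.19 and 3.21 and Listing 2 record the stop. No safety incidence, PK estimate, crossover contrast or analysis population changes. The number misclassified cannot be known from the documents. The Part 3 range of 0 to 6 of 18 assumes that about 18 are treated and that any early stops stay within the allowance. No comparable allowance is stated for Part 1. If nobody stops early, the tables will be right, but only by coincidence.

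**What to change.** Change the four footnotes and the derivation behind them. Treatment status is complete only if the participant was dosed in every period planned for that participant. Otherwise report discontinuation with its reason and period, consistent with Listing 2.

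In Part 3 the planned number is three. In Part 1 it should be the participant's own planned periods. A fixed count of three, or four with 800 mg, would misclassify replacements who start mid-sequence. It would also misclassify anyone planned only for the 800 mg period.

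One reconciliation is needed first. SAP section 2.3 describes nine new, previously unexposed participants for 800 mg, while Protocol section 4.1 draws them from Cohorts 1 and 2. The documents must agree on who enters that period before planned periods can be defined.

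The cost is four footnotes and one derivation. Dosing dates and times are already recorded (Protocol section 6.5) and discontinuation reasons are already planned for Listing 2, so no new data are needed.
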